#### Anterior knee pain provocation test

The anterior knee pain provocation test is a unilateral self-performed and self-rated test, designed to provoke known anterior knee pain. Only the affected or most affected knee is tested. In the control group, the “affected leg” is decided by coin toss.

The participant will be instructed to *stand on the affected leg, with the non-affected side against the wall, and their back straight*. The back of the hand is held against the wall as support. They will then be instructed to stand in a static single-legged squat position, with knee flexion about 60°, while the other leg is extended forward above the ground. The position is held for 45 sec and timed with a stopwatch. Standardized verbal instruction is provided before each trial by the tester: *are you ready to start the test? Start... and stop.*

Participants will provide their perceived pain intensity immediately before and after completing the 45s. hold.

#### Counter Movement Jump Test

The counter movement jump test measures jump height(cm), power(watt), and pain during trial (NRS 0-10). Increased countermovement jump height is associated with increased sprint performance, lower body power and enhanced force-velocity. Likewise, the test is found feasible for adolescents.

The participant is standing with their legs shoulder width apart, and with their hands placed on their hips. They will be instructed to *jump straight up and down, and as high as possible*. One test trial is conducted, and three trials where measurements are made.

Standardized verbal instruction is provided before each trial by the tester: *are you ready to jump? Go.* There will be a 30second rest between each attempt. After each test jump a written NRS is made by the participant, hidden from tester HS.

The attempts are recorded using the slow-motion function (>240frames per second) on a fixated iPhone. To analyse the recordings, the smartphone application MyJump 2 is used for a highly reliable slow-motion video analysis.

Data will be normalized per MyJump 2 procedures to push-off distance (distance from the floor to trochanter major in a 90° squat position) combined with leg length (measured prone from the superior anterior iliac spine to the tiptoes in full plantar flexion). The mean of three trials will be used.

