## Hypotheses

The hypotheses being tested are

1. that adolescents with Osgood-Schlatter, has a lower knee extension RTD in their affected knee compared to matched controls
2. that adolescents with Osgood-Schlatter, has a lower knee extension RTD in their affected knee compared to their potential asymptomatic knee
3. that adolescents with Osgood-Schlatter, has a lower knee extension RTD in their potential asymptomatic knee compared to matched controls
4. that adolescents with Osgood-Schlatter, has a lower knee flexion RTD in their affected knee compared to matched control
5. that adolescents with Osgood-Schlatter, has a lower knee flexion RTD in their affected knee compared to their potential asymptomatic knee
6. that adolescents with Osgood-Schlatter, has a lower knee flexion RTD in their potential asymptomatic knee compared to matched controls
7. That levels of either early or late rate of torque development is negatively correlated with pain during rate of torque development-testing, countermovement jump height or power, anterior knee pain provocation test score, current pain, pain duration, KOOS child 'Pain', 'Sport/rec' or 'QoL' subscales,

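### Jump power is built from two lengths taken from different hip landmarks, with no formula for combining them; if they are subtracted, this understates absolute watts (minor)

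*Combined protocol and SAP*

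**What the plan says.** The section on the Counter Movement Jump Test lists three outputs: "The counter movement jump test measures jump height(cm), power(watt), and pain during trial (NRS 0-10"). It then says "Data will be normalized per MyJump 2 procedures to push-off distance". The text that follows describes that distance, and the length it is joined with, as "distance from the floor to trochanter major in a 90° squat position) combined with leg length (measured prone from the superior anterior iliac spine"; leg length runs from there to the toes with the foot fully pointed.

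No equation is given for the combination. The instruction to the child is to "jump straight up and down, and as high as possible", with no depth specified.

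Power is used in one place, hypothesis 7, which proposes that RTD "is negatively correlated with pain during rate of torque development-testing, countermovement jump height or power", among other variables. It is not listed under Outcome measures, nor among the variables compared between groups under Statistical methods.

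**The concern.** Push-off distance is the rise of the body from the bottom of the squat to take-off. It can be obtained as the difference of two lengths, but only if both start from the same point on the body. Here one starts at the trochanter major and the other at the anterior iliac spine, which lies higher on the pelvis. The difference therefore also contains the vertical gap between the two.

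Two further features make the input hard to reproduce. Read literally, the bracket labels the squat height itself as push-off distance, which is another quantity. And leg length is taken prone, when the front of the pelvis faces the table.

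At stake are the accuracy and reproducibility of the reported watts, in a study that plans to share its full data set.

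**Working it through.** The documents state no figure for power or push-off distance, so there is none to reproduce. The check asks how far the landmark mismatch moves computed power.

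**Inputs**
- From the jump test section: the two landmarks, the 90° squat, and no set jump depth.
- Assumed, because the documents do not give them: combination by subtraction; jump height h = 0.20-0.30 m; true push-off distance d = 0.30-0.40 m; iliac spine-to-trochanter gap e = 5-12 cm; body mass m = 50 kg where watts are shown.
- Also assumed: that power is mean push-off power from mechanics. The protocol does not say how the app derives watts.

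**Step 1: geometry.** Let T be trochanter-to-toe length and S the trochanter height in the squat. The distance wanted is d = T − S. Leg length from the iliac spine is T + e, so the plan's two lengths give (T + e) − S = d + e.

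**Step 2: power.** Work done is m·g·(h + d). Push-off time is 2d/v, with v = √(2gh). Hence P = m·g·(h/d + 1)·√(g·h/2), which falls as d rises. Mass and gravity cancel in the ratio:

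P(d + e) / P(d) = [h/(d + e) + 1] / [h/d + 1]

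**Step 3: numbers**

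| Case | h (m) | d (m) | e (m) | Ratio | Change |
|---|---|---|---|---|---|
| Smallest | 0.20 | 0.40 | 0.05 | 1.444/1.500 = 0.963 | −3.7% |
| Example | 0.25 | 0.35 | 0.08 | 1.581/1.714 = 0.922 | −7.8% |
| Largest | 0.30 | 0.30 | 0.12 | 1.714/2.000 = 0.857 | −14.3% |

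For a 50 kg child, the example is 931 W with one landmark and 859 W with two. On a wider grid (h 0.15-0.30 m, d 0.25-0.40 m, e 4-12 cm) the change runs from −2.5% to −17.7%.

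**Step 4: the literal reading.** If a squat height of 0.45-0.55 m (assumed) were itself entered as push-off distance, the same ratio gives:
- 1.444/1.500 = 0.963, or −3.7% (h 0.20, d 0.40, entered 0.45);
- 1.545/2.000 = 0.773, or −22.7% (h 0.30, d 0.30, entered 0.55).

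**Step 5: total error when the child does not jump from 90°.** Take h = 0.25 m, a 90° value of 0.30 m and a gap of 8 cm. The entered distance is 0.38 m, so the numerator is 0.25/0.38 + 1 = 1.658.
- True travel 0.25 m: 1.658/2.000, −17.1%
- True travel 0.30 m: 1.658/1.833, −9.6%
- True travel 0.38 m: 0%
- True travel 0.45 m: 1.658/1.556, +6.6%

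**Step 6: effect on hypothesis 7.** An illustrative simulation of 200,000 children used assumed means (SDs): h 0.25 (0.05) m, d 0.32 (0.04) m, mass 50 (10) kg, gap 8 (1.5) cm. Mean power fell by 8.8%, but power with and without the mismatch correlated at 0.996. If the gap is otherwise unrelated to RTD, a correlation shrinks by about that factor: 0.500 becomes 0.500 × 0.996 = 0.498. For comparison, the standard error of a correlation on the Fisher z scale is 1/√(26 − 3) = 0.21 with 26 participants and 1/√(13 − 3) = 0.32 with 13.

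**The case against.** The strongest reply is that the protocol defers to the app's own procedures and never states a subtraction, so both the formula and the size of the error are supplied by the reviewer. That is correct, and it limits the claim to a conditional one. It does not remove the point: the protocol names its own landmarks, they differ, and an assessor cannot get one reproducible push-off distance from the sentence.

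The second reply is that nothing important depends on watts. This largely stands. Power is one correlate among several, and a near-common shift hardly alters a correlation.

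Three stronger readings are tempting, and the documents do not support them.
- *Every child's power is biased low.* No formula is given and jump depth is not set. Step 5 shows that travel beyond the 90° value can cancel or reverse the error.
- *Painful children dip less, so the error is related to pain and distorts hypothesis 7.* The documents say nothing about how pain changes jump depth, and using one landmark would not cure such an error.
- *Jump height should therefore become the lead jump correlate.* Hypothesis 7 already names both height and power, so ranking them would be a preference and does not follow from the landmark mismatch.

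The prone posture may be a slip of wording. It makes the landmark awkward to reach but gives no direction of bias.

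**Conclusion.** The point holds in a limited form. The two lengths use different proximal landmarks and the plan does not say how they are combined. Under subtraction, the mismatch by itself overstates push-off distance and understates absolute power by roughly 4% to 14%. That range rests wholly on the assumed gap, jump height and push-off distance, and on the mechanical power formula. It describes one component of the error, not the net error for any one child.

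The hypothesis 7 correlations would barely move. Jump height does not use these lengths in the text, and no RTD outcome or group comparison depends on them. Severity is minor: the gain is in correct and reproducible watts.

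**What to change.** In the Counter Movement Jump Test section:
- measure both lengths from the trochanter major;
- take leg length to the tiptoes in full plantar flexion, in a posture where the trochanter can be reached;
- state that push-off distance equals this leg length minus trochanter height in the 90° squat.

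This costs one sentence and a different tape point, with no extra participants, staff or testing time. It removes the landmark component of the error only. Variation in actual jump depth remains and could be noted as a limitation wherever watts are reported.

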#### Patient Reported Outcome Measures

Participants will fill out a questionnaire, containing some basic information about their pain experience, such as: duration of pain, previously received treatment, current pain, worst pain during past 24 hours and week. Furthermore, there are questions about activity level, as well as questions from Knee Injury and Osteoarthritis Outcome Score (KOOS-child) and Tampa Scale of Kinesiophobia (TSK-17).

#### KOOS

KOOS is used for patients with knee pain and injuries. The questionnaire contains questions within five categories: symptoms, pain, physical function in daily life, physical function during sports and activities, and life quality. In this study, participants will fill out questions from the ‘Sport/rec’ and

‘Quality of Life’ subscales, and questions P1, P4, P6a, and P6b from the ‘Pain’ subscale. Questions are answered on a 1-4likert scale in normalized to a 0-100 score for each subscale with 100 being the optimal score.

#### TSK-17

The Tampa scale is a 17-item questionnaire to evaluate fear avoidance behaviour in patients experiencing pain. It consists of two subscales, activity avoidance and somatic focus. The questions are rated on a 1-4 likert scale by the patient. The sum of the points are ranged from 17-68points, with above 37 being defined as “high levels of kinesiophobia”. All questions are used in the questionnaire.

### Outcome measures

The outcome measures are rate of torque development and NRS-values in relation to the force-measurements. To calculate the rate of torque (Nm/s/kg), the rate of force development-variables (N/s) is multiplied with length of the lever (m) and divided with the participant's bodyweight (kg).

Outcome variables related to the specified hypotheses are rate of torque development during 0-100 ms, 0-200 ms, peak RTD, and time to peak force during knee extension and knee flexion for both cases and controls.

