## Background

Osgood-Schlatter is a growth-related condition involving multiple types of tissue in the tendon-bone interface at the tibial tubercle. Osgood-Schlatter affects one in ten adolescents causing persistent pain, reduced peak torque during knee extension, and reduced ability to maintain participation in sports and physical activity. Rate of torque development is linked to athletic performances, and reductions in rate of torque development is associated with decreased neuromuscular functioning and pain chronicity. As peak torque is reduced in Osgood-Schlatter, changes in rate of torque development is likely also affected, but this has not yet been investigated. This insight could help characterize the condition and guide management.

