## Expected results and implications

As the condition affects the knee-extensor mechanism, we expect lower levels of rate of torque development in the affected knee during extension. The main interest, however, is if the level of rate of torque development is also significantly reduced in non-symptomatic limbs or in knee flexion, in cases compared to symptom-free healthy controls. This would indicate inhibited neuromuscular function on a central level, due to other factors than local tissue pathology, such as pain chronicity, central muscle inhibition, or other drivers.

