### Statistical considerations

#### Sample size

No previous investigations of rate of torque have been published for adolescents with Osgood-Schlatter. One previous study using the same clinical test setup, equipment, and time-epochs (Early RTD: 0-100 ms, Late RTD: 0-200 ms, and peak RTD) for testing RTD over the hip in young (Under-19) professional soccer players found a mean of 9.57 Nm/kg/s and a standard deviation of 2.6 Nm/s/kg at 0-100 ms.

Considering that peak torque is around 30-50% lower for adolescents (U13 and U14) compared to U19 players, a similar difference might be expected for RTD, and thus we expect a group mean RTD of around 5 or 6 Nm/kg/s at 0-100 ms for asymptomatic adolescents. In adults with non-traumatic knee pain, investigations of RTD during maximal isometric hip extension, has shown differences between symptomatic participants and controls of >50 % during early RTD.

As this study includes RTD of the knee, which is the affected joint, we expect at least similar differences for our primary measure, early RTD at 0-100 ms, this would correspond for example to a between-group difference of 6 vs. 3 Nm/kg/s. We will assume 2.6 Nm/kg/s as an asymptomatic population standard deviation for 0-100 ms. Based on a two-sided two-sample t-test at 80% power and 5% alpha level, 13 participants in each group would thus be needed to detect a 50% between-group difference (R 4.0.2, Foundation for Statistical Computing, Vienna, Austria; RStudio 1.0.153, power.t.t.test package).

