## Statistical methods

The outcome variables (rate of torque development 0-100 ms, 0-200 ms, peak RTD, time to peak RTD, time to peak torque for both knee extension and knee flexion, respectively) will be compared between groups using an unpaired two-sided students t-test, assuming the residuals will be normally distributed, otherwise the non-parametric alternative, the Wilcoxon rank sum test, will be used. The alfa and beta-1 level will be set for 5% and 80%, respectively.

As outcome variables have been a priori specified and prioritized, and also analyzed and reported in the pre-specified order, no corrections for multiple testing will be applied. Data will be reported with between-group differences, standardized effect sizes based on Cohens d, exact p-values, and 95% confidence intervals. All data inspection, analysis, and visualizations will be conducted using R (R Foundation for Statistical Computing, Vienna, Austria), in the jamovi interface (The jamovi project 2023, version 2.4.1). All r-code and full data set will be shared with journal publication or in an open-access repository.

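### Absolute RTD per kg cannot by itself support the central-inhibition reading, because lower maximal strength lowers it too and no planned analysis is set up to separate the two

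*Combined protocol and SAP*

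**What the plan says.** The Outcome measures section defines the outcome set as follows: "Outcome variables related to the specified hypotheses are rate of torque development during 0-100 ms, 0-200 ms, peak RTD, and time to peak force", for both movements and both groups. Statistical methods gives nearly the same list, with one more timing variable: "rate of torque development 0-100 ms, 0-200 ms, peak RTD, time to peak RTD, time to peak torque". Force rate is converted to torque rate by multiplying by lever length and dividing by bodyweight. The participant's own maximum does not enter. Peak torque appears in neither list, nor under Descriptive variables.

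The Background counts reduced strength among the features of the condition: "persistent pain, reduced peak torque during knee extension, and reduced ability to maintain participation in sports and physical activity". It then argues from strength to RTD: "As peak torque is reduced in Osgood-Schlatter, changes in rate of torque development is likely also affected". The Sample size section reasons the same way across age groups. Having noted that peak torque is 30-50% lower in younger players, it says that "a similar difference might be expected for RTD".

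Expected results and implications puts the main interest in non-symptomatic limbs and in flexion. Of a lower RTD there it says: "This would indicate inhibited neuromuscular function on a central level, due to other factors than local tissue pathology". Pain chronicity and central muscle inhibition are among the examples it gives.

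Under Knee extension, three maximal attempts are recorded, each held for about 3-4 s.

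**The concern.** Absolute RTD reflects two things: how high the torque-time curve goes and how quickly it gets there. A weaker muscle activated at a normal relative rate has a lower absolute RTD. The plan relies on this link when it expects RTD to fall with peak torque, but it does not consider the link when it interprets a group difference.

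The stake is the conclusion, not the test. A lower RTD in the asymptomatic limb or in flexion could be published as evidence of central inhibition when the data are equally compatible with lower maximal strength in those muscles. Better matching on activity would make a strength difference less likely, but it would not separate the two explanations if one were present.

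**Working it through.** **Inputs.** From Sample size: control mean 5 or 6 Nm/kg/s at 0-100 ms, planned contrast 6 vs 3, SD 2.6, 13 per group, two-sided 5% t-test, 80% power. Assumed: the size of any peak-torque deficit (10-50%), because the documents give none for this condition.

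**1. The plan's own figure.** d = 3/2.6 = 1.154. The noncentral t calculation gives n = 12.83, rounded up to 13 per group, with power 80.6%. The sample size is reproduced and is not at issue.

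**2. The plan's own scaling.** The reference value is 9.57 Nm/kg/s in under-19 players. 9.57 × 0.70 = 6.70 and 9.57 × 0.50 = 4.79. The plan's expected 5 or 6 lies in that range, so the sample size treats RTD as tracking peak torque.

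**3. Effect of strength alone.** Write T(t) = Tmax × g(t), with g the curve shape. Then RTD(0-100 ms) = Tmax × g(0.1)/0.1. The 0-200 ms and peak values also carry Tmax as a factor, so an x% fall in Tmax gives an x% fall in all three. RTD divided by Tmax is unchanged, and so are the times to peak.

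Power of the planned t-test on RTD 0-100 ms, 13 per group, SD 2.6 in both groups as in the plan:

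| Lower maximal torque | Control mean 5: case mean, power | Control mean 6: case mean, power |
|---|---|---|
| 10% | 4.5, 7.6% | 5.4, 8.7% |
| 20% | 4.0, 15.6% | 4.8, 20.4% |
| 30% | 3.5, 29.2% | 4.2, 39.5% |
| 40% | 3.0, 46.9% | 3.6, 61.7% |
| 50% | 2.5, 65.3% | 3.0, 80.6% |

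If strength loss also shrank the spread among cases, power would be somewhat higher.

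**4. Strength loss against slowing.** For illustration, assume T(t) = Tmax(1 − exp(−t/τ)) with Tmax = 2.0 Nm/kg and τ = 0.15 s. Compare halving Tmax with slowing the rise (τ = 0.36 s) until RTD 0-100 ms is also halved. This curve has no exact peak, so time to 95% of maximum stands in for time to peak.

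| | Reference | Half strength | Slower rise |
|---|---|---|---|
| RTD 0-100 ms (Nm/kg/s) | 9.73 | 4.87 | 4.87 |
| RTD 0-200 ms (Nm/kg/s) | 7.36 | 3.68 | 4.27 |
| Peak RTD (Nm/kg/s) | 13.33 | 6.67 | 5.58 |
| RTD 0-100 ms / Tmax (per s) | 4.87 | 4.87 | 2.43 |
| Time to 95% of maximum (s) | 0.45 | 0.45 | 1.07 |

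The primary measure is the same in both scenarios. Relative RTD and timing differ. The pattern across the three magnitudes differs only modestly: falls of 50%, 50% and 50% under strength loss, against 50%, 42% (1 − 4.27/7.36) and 58% (1 − 5.58/13.33) under slowing.

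**The case against.** Four parts of the opposing case stand.

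First, a reader might infer that the trial has no means at all of telling slow from weak. The documents do not support that. The analysis list includes "time to peak RTD, time to peak torque for both knee extension and knee flexion, respectively", and under the model above these outcomes are unaffected by strength. They are weak for the purpose, however. Time to peak torque comes from a 3-4 s push rather than the first 100-200 ms. Time to peak RTD is listed only under Statistical methods and is resolved in 10 ms steps at 100 Hz. No hypothesis names either one, and no rule links them to the interpretation.

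Second, a reader might infer that the plan would call a deficit in the affected knee central. It does not: it expects that deficit because the condition affects the extensor mechanism, and it keeps the central reading for non-symptomatic limbs and flexion. In those places no peak-torque deficit is documented, since the Background states one only for knee extension. A strength explanation there is possible, not established.

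Third, hypotheses 1-6 ask only whether RTD is lower, and the planned outcomes answer that.

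Fourth, strength and inhibition are not exclusive alternatives. Inhibition can itself lower voluntary peak torque. If it scaled the whole curve, relative RTD would look normal. So it would be wrong to conclude that the cause is reduced strength whenever relative RTD does not differ, and more so because a non-significant result at 13 per group shows little.

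The table of strength deficits also rests on a proportionality assumption and is not evidence that such a deficit exists. At deficits of 20-30% it would usually not reach significance.

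**Conclusion.** The point holds as a matter of interpretation. All RTD magnitudes are absolute values per kg, peak torque and relative RTD are not analysed, and no planned analysis is set up to separate slower torque development from lower maximal strength. The central-inhibition inference in Expected results and implications would therefore not be supported by absolute RTD alone.

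The size depends on an unknown. A 50% strength deficit with a control mean of 6 would reproduce the whole planned effect. Smaller deficits would contribute in proportion and add to any true slowing. This assumes an unchanged curve shape and the plan's SD of 2.6. The primary measure, hypotheses 1-6 and the sample size are not faulted.

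**What to change.** Keep absolute RTD 0-100 ms as the primary measure and leave the sample size unchanged.

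In Outcome measures and Statistical methods, pre-specify three supportive outcomes from the attempts already recorded: peak torque (Nm/kg), and RTD 0-100 ms and RTD 0-200 ms, each divided by that attempt's own peak torque. Bodyweight and lever arm cancel in the ratio, which is expressed per second. Summarise over the three attempts in the same way as absolute RTD, and report estimates with 95% confidence intervals.

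Qualify Expected results and implications. If absolute RTD is lower but relative RTD is not clearly lower, report that the deficit cannot be distinguished from lower maximal strength. Make no specific claim about rate of activation or central inhibition, and do not conclude that reduced strength is the cause.

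The cost is wording and a little code. No extra testing appears necessary, because finding the time to peak force already requires locating that peak in each trace. The downsides are three supportive outcomes for each of the six comparisons (3 × 6 = 18 estimates) without multiplicity correction, and a more restrained conclusion. Specifying them now matters, because relative RTD added after the data are seen would be one more unadjusted post hoc choice.
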